8 STATISTICS AND DATA ANALYSIS

8.1 SAMPLE SIZE CALCULATION

Power calculations were performed utilising G-Power 3.1 (Faul et al., 2007). The statistical analysis was set to be a with a within-between interaction, with two groups and three measurement points. The alpha level was set to 0.05 and power to 0.80, as per convention (Cunningham & McCrum-Gardner, 2007). The effect size previously reported for psychological distress in a similar study (McConachie et al., 2014) was medium to large. To be conservative, the power calculation for this study was performed with a medium effect size ($f=0.25$), which suggested a total sample size of 28 participants. Therefore, this study will aim to have four groups with ten participants each. This would mean recruiting 40 participants, with the expectation that 12 would be lost to attrition.

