8.2 PROPOSED ANALYSES

Summary Measures Reported

The mean, standard deviation and range of the demographic variables and dependent variables will be reported. The percentage of missing data across the measures will also be reported.

Methods of Analysis

Regarding quantitative data, the statistical analysis will be completed using SPSS software. Data will be explored to ensure that test assumptions are met. Each dependent variable will then be analysed with repeated measures analyses of variance (ANOVA) with a within-between interaction, with significant effects further evaluated appropriately.

Regarding qualitative data, the focus group interview transcripts will be analysed with thematic analysis, as per Braun and Clarke (2006).

Management of Missing Data

Should the level of missing data be minimal (<5%), the data will be assumed to be missing at random and a suitable method of imputation (most likely multiple imputation due to the small sample size) will be used to manage this appropriately.

Should a higher level of missing data occur, the missing data will be analysed to examine whether it is missing at random or not. A suitable method of imputation will then be used.

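### Section 8.2 pairs imputation with a repeated-measures ANOVA but gives no rule for combining the F tests; a small-sample-corrected mixed model on all observed scores is a cheap improvement

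*Combined protocol and SAP*

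**What the plan says.** Section 8.2 (Methods of Analysis) states: "Each dependent variable will then be analysed with repeated measures analyses of variance (ANOVA", and the model includes the within-between interaction. SPSS is the software, and the statement covers every outcome, including the primary DASS-21.

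Section 8.2 (Management of Missing Data) has two branches. Below 5% missing, "a suitable method of imputation (most likely multiple imputation due to the small sample size) will be used". Above that, the missingness is examined first and an unnamed suitable imputation method follows. Neither branch says how results from several imputed data sets become one test.

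Section 8.1 sizes the study for a design "with a within-between interaction, with two groups and three measurement points" and ends: "This would mean recruiting 40 participants, with the expectation that 12 would be lost to attrition".

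Two other sections bear on who is imputed. Section 5.2.1 leaves people who miss one or more sessions out of relevant analyses, without saying which analyses those are. Section 6.2 posts the follow-up questionnaires to people who do not attend the focus group.

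**The concern.** Multiple imputation produces several completed data sets, each with its own F statistic. Unless a combining rule is fixed in advance, an analyst could test a single imputed data set, average the imputations into one file, average the F values, or take a typical p value. Each of these treats imputed scores, wholly or partly, as if they had been observed, and so understates the uncertainty. The imputed data sets may also fall on both sides of 0.05 with nothing to decide between them.

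The alternative is to analyse completers only. That is safe when loss is unrelated to the scores, but not when people with particular baseline scores leave more often.

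The documents describe no untreated control arm, so the test of change over time on DASS-21 carries much of the effectiveness question in section 2.1.1. The false-positive rate of that test should not depend on a choice made after the data are seen.

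**Working it through.** **Inputs from the documents.** Alpha 0.05, power 0.80, f = 0.25, k = 2 groups, m = 3 times, N = 28, 40 recruited, 12 lost (all section 8.1); repeated-measures ANOVA (section 8.2). Correlation between times, sphericity, and the pattern and mechanism of loss are not given, so they are assumed below.

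**Step 1: the plan's own figure.** For a within-between interaction, λ = f²·N·m/(1−ρ), df1 = (k−1)(m−1) and df2 = (N−k)(m−1). With ρ = 0.5 and ε = 1 (assumed), λ = 0.0625 × 28 × 3 / 0.5 = 10.5, df1 = 2 and df2 = 26 × 2 = 52. Power is 0.812, so 28 is reproduced. Other correlations give N = 54 (ρ = 0), 38 (0.3) and 18 (0.7). Recruitment: 28/(1 − 12/40) = 28/0.70 = 40.

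**Step 2: which missing-data branch applies.** Forty people at three times give 120 planned scores.
- If all 12 miss only the last score: 12/120 = 10%.
- If 6 miss both later scores and 6 only the last: (6 × 2 + 6)/120 = 18/120 = 15%.
- If all 12 miss both: 24/120 = 20%.

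If the 12 stay in the analysis, the study is in the higher branch, where no imputation method is named.

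**Step 3: false-positive rates.** The simulation used no true effect, 40 people (20 + 20), compound symmetry and 12 lost. Five scenarios combined ρ of 0.5 or 0.7; loss of both later scores by all 12, or the 6/6 split; and loss completely at random or dependent on baseline. There were 4,000 runs per scenario (Monte Carlo SE √(0.05 × 0.95/4000) ≈ 0.35 percentage points). Imputation was sequential Bayesian regression with 20 or 5 imputations. Ranges cover the scenarios and, unless stated, both the time and the interaction tests.

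| Analysis | False positives at nominal 5% |
|---|---|
| ANOVA, no data missing | 4.4% to 5.4% |
| One stochastically imputed data set | 13% to 22% |
| Single regression imputation | 14% to 24% |
| Imputations averaged into one data set | 14% to 24% |
| F values averaged informally | 11% to 20% |
| Median p value | 10% to 16% |
| Last observation carried forward, loss completely random | 4.3% to 5.4% |
| Last observation carried forward, time test, loss depends on baseline | up to 8.3% |
| Multiple imputation pooled by D1 | 3.2% to 4.9% |
| Multiple imputation pooled by D2 | 3.7% to 5.0% |
| Completers only, loss completely random | 4.4% to 5.6% |
| Completers only, time test, loss depends on baseline | 8.5% to 11.7% |
| Mixed model, Kenward-Roger | 4.5% to 6.0% |
| Mixed model, uncorrected Wald, unstructured covariance | 6.9% to 8.6% |
| Mixed model, uncorrected Wald, compound symmetry | 5.4% to 6.2% |

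The two completers figures for baseline-dependent loss are 11.7% (ρ = 0.5, 6/6 split) and 8.5% (ρ = 0.7, all 12 missing both). The interaction test stayed at 5.1% and 4.7% in those scenarios.

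**Step 4: cross-check.** A separate simulation of the time test used five imputations and the 6/6 split. At ρ = 0.5 and 0.7 it gave 13.7% and 14.9% on one imputed data set, and 14.2% and 16.2% on the average of five. The five data sets disagreed about p < 0.05 in 25.8% and 29.3% of trials.

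**Step 5: precision.** Under the 6/6 split at ρ = 0.5, using all observed scores rather than completers multiplies the standard error of change from baseline by 0.954 at follow-up and 0.890 at session 3. These are reductions of about 5% and 11%.

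**The case against.** A reader might infer that the ANOVA F test cannot be pooled over imputations, so that the test and the missing-data method are incompatible. That is wrong: D1 and D2 are established rules for multi-degree-of-freedom tests, and both held the rate at or below 5% here. The documents do not reject such a rule; they name none. Whether SPSS would pool this F test automatically cannot be checked from the documents.

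A reader might also infer that the planned analysis has a 13% to 24% false-positive rate. The documents do not support that either, for three reasons.

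- Multiple imputation is named only for the branch below 5% missing. In a further simulation, testing one imputed data set or the average of five gave 6.0% to 6.4% with 2.5% of scores missing and 7.5% to 7.7% with 5% missing.
- Section 8.1 counts on 28 people remaining and section 5.2.1 excludes people who miss a session, so some or all of the 12 may never be imputed. If all are dropped and loss is completely random, the test is sound.
- The postal questionnaires in section 6.2 should reduce the number who lack only the follow-up scores.

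These points make the inflation conditional but do not close the gap. Someone who attends every session can still fail to return follow-up questionnaires, and the time test on completers is not protected when loss depends on baseline. Finally, a mixed model is not the only remedy, since naming D1 or D2 would also control the error, and the mixed model needs a small-sample correction to do so.

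**Conclusion.** The point holds as a gap in specification. Section 8.2 imputes by a method that is unnamed once missing data reach 5%, then runs a complete-data test, and gives no combining rule. What happens to the false-positive rate depends on choices left open. It is about 13% to 24% if the 12 expected losses are imputed and analysed as one or an averaged data set. If they are dropped, the time test is near 5% under completely random loss and about 8.5% to 11.7% when loss depends on baseline. With D1 or D2 it is at or below 5%.

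These figures rest on assumed correlations (0.5 and 0.7), compound symmetry, a 20 + 20 split and assumed loss patterns. They do not establish what the trial's error rate will be, because the documents do not say how many of the 12 would be imputed and how many excluded. The point is a cheap improvement, not an error that must be fixed.

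**What to change.** In section 8.2, make the primary analysis a linear mixed model for repeated measures, fitted by REML, with time, participant type and their interaction, unstructured covariance, and Kenward-Roger or equivalent small-sample degrees of freedom. Fit it to all observed scores with no prior imputation. Report mean change from baseline at session 3 and at six weeks with 95% confidence intervals. The unstructured covariance also removes the sphericity assumption.

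Keep multiple imputation as a sensitivity analysis that pools those mean changes; if F tests are kept, name D1 or D2 in advance.

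Reconcile this with section 5.2.1: define the relevant analyses, and say whether people who miss a session are excluded from the primary analysis or contribute the scores they have. As it stands, that exclusion conflicts with using every observed score.

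The cost is SAP wording, with no new data and the same software. The downsides are slightly more modelling work and an estimated covariance in a small sample. The small-sample correction is essential: without it the mixed model ran at 5.4% to 8.6%. Only Kenward-Roger was simulated, so confirm which correction the installed SPSS release offers before fixing the wording.

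### Section 8.2 rests on a missing-at-random check that observed data cannot settle, plans no sensitivity analysis, and with section 5.2.1 leaves open whether the expected 30% lost are imputed or dropped

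*Combined protocol and SAP*

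**What the plan says.** All places are in the combined protocol and SAP.

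- **Section 8.2, low missingness:** "Should the level of missing data be minimal (<5%), the data will be assumed to be missing at random", and the data are then imputed, most likely by multiple imputation.
- **Section 8.2, higher missingness:** "the missing data will be analysed to examine whether it is missing at random or not". The next sentence is "A suitable method of imputation will then be used". No test, criterion or imputation model is given for this branch, and nothing is said about what changes if the answer is no. No sensitivity analysis appears anywhere.
- **Section 8.1:** the calculation is for a within-between interaction "with two groups and three measurement points", "which suggested a total sample size of 28 participants". Forty are to be recruited, "with the expectation that 12 would be lost to attrition".
- **Section 5.2.1:** a participant who misses one or more sessions may still attend the rest but is left out of the analyses concerned. Withdrawal option (ii) removes all of that person's data. The reason for withdrawal is recorded where possible.
- **Section 6.2:** follow-up questionnaires are posted to those who do not come to the focus group.
- **Section 8.2, summary measures:** the percentage of missing data is reported.

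**The concern.** Missing at random means that, given what was observed, the chance of a score being missing does not depend on its value. That value is exactly what is not available. Examining the observed data can show that drop-out is related to baseline distress or role, which helps in choosing imputation variables. It cannot show whether drop-out also depends on later, unrecorded distress. The plan treats the question as answerable and offers nothing for the case where the assumption fails.

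The primary outcome is the DASS-21 and the primary objective is a reduction in distress. Section 1.1 accepts that taking part may itself cause some distress, so drop-out linked to poor response is plausible. If it happens, the people whose scores are missing are those who did worse, and both imputation under missing at random and simple exclusion would make the fall in distress look larger than it was. A non-significant comparison of drop-outs with completers could then be read as reassurance that it does not give.

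**Working it through.** **1. The plan's own figures.** From section 8.1: "The alpha level was set to 0.05 and power to 0.80, as per convention", two groups, three time points, f = 0.25. The text gives neither the correlation between repeated measures nor the sphericity correction; assume 0.5 and 1.

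- Noncentrality = N × 3 × f² / (1 − 0.5). For N = 28: 28 × 3 × 0.0625 / 0.5 = 10.5, with 2 and 52 degrees of freedom. Power is 0.812.
- For N = 26 it is 9.75 and power is 0.778. So 28 reproduces.
- Attrition: 12/40 = 30%, and 28/(1 − 0.30) = 40. This also reproduces.

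**2. What a baseline check could detect.** Compare 12 drop-outs with 28 completers, two-sided alpha 0.05. Noncentrality = d × √(12 × 28/40) = d × 2.898.

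- d = 0.5 SD: 1.449, power 0.292.
- d = 0.3 SD: 0.869, power 0.135.

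This assumes that all 12 have a baseline score. Anyone lost while waiting for a group would have none.

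**3. Size of the possible bias in mean change.** With imputation under missing at random, bias = share missing × mean amount by which the unseen scores exceed their prediction. The simulation has standardised baseline and follow-up scores, no true change, 30% missing at follow-up, and logistic drop-out driven by the unseen follow-up score. Slopes (log-odds per SD) and correlations are assumptions; the documents give none.

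| Slope | Correlation | Unseen minus predicted (SD) | Bias, imputation (SD) | Bias, exclusion (SD) |
|---|---|---|---|---|
| 0.69 | 0.5 | 0.481 | −0.144 | −0.094 |
| 1.0 | 0.5 | 0.650 | −0.194 | −0.122 |
| 1.5 | 0.5 | 0.869 | −0.260 | −0.164 |
| 0.69 | 0.7 | 0.336 | −0.100 | −0.056 |
| 1.0 | 0.7 | 0.463 | −0.138 | −0.076 |
| 1.5 | 0.7 | 0.625 | −0.186 | −0.096 |

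Hand check: 0.30 × 0.481 = 0.144; 0.30 × 0.336 = 0.101. Negative means a false fall in distress. Widening the assumptions to slopes of 0.5 to 1.5 and correlations of 0.5 to 0.75, with exactly 12 of 40 lost and the chance of loss weighted on the log scale, gives about 0.07 to 0.29 SD for imputation and 0.04 to 0.18 SD for exclusion. How the losses are drawn moves the ends by a few hundredths.

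**4. Effect on a test of change (N = 40, no true change, nominal 5%, slopes and correlations as in the table).** A pre-post test rejects in about 9% to 26% of trials after multiple imputation and in about 6% to 15% with exclusion.

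**5. Does the check separate harmless from harmful?** The baseline comparison is significant in 42% to 93% of trials when drop-out depends only on observed baseline distress, where imputation has bias of about zero and rejects in 4% to 6%. It is significant in only 15% to 61% when drop-out depends on unseen distress, where imputation is biased. It tends to flag the harmless case more often.

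**6. Exclusion is not neutral either.** When drop-out depends only on baseline distress, exclusion gives a bias of +0.06 to +0.17 SD, in the opposite direction.

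**7. Interaction.** With 20 per group, 6 lost in each and the same drop-out mechanism, the bias in the group-by-time contrast is about 0.004 to 0.007 SD, effectively zero.

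**The case against.** The best reply is that section 8.1 powers for 28 and recruits 40, which fits a plan to analyse those who stay. Read with section 5.2.1, many of the 12 would be excluded, and section 8.2 would only fill gaps among those analysed. On that reading the under-5% branch might still apply, so a reader who infers that it cannot, or that all 12 will be imputed, goes beyond the text. That part stands. It does not rescue the plan: the two sections are not reconciled, and exclusion can also bias the result.

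Four further limits stand.

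- **Bias is possible, not certain.** A reader might infer that the result will be biased. If drop-out depends only on measured baseline distress, and that is in the imputation model, the bias is about zero.
- **The wording permits a method chosen after the check.** That could include one that does not assume missing at random. The text is unspecified, not committed to the wrong method.
- **Some safeguards exist.** Posted questionnaires, recorded withdrawal reasons and the reported percentage missing would make the loss visible. None tests whether the conclusion survives worse outcomes among those lost.
- **The simulation is simplified.** It uses two time points and a pre-post test, and represents exclusion as loss of the follow-up score. If loss occurs only at six weeks and session-3 and six-week scores correlate 0.7 to 0.8 (assumed), imputation bias falls to about 0.05 to 0.18 SD.

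It is also tempting to express the bias as a share of the planned effect. The f = 0.25 in section 8.1 is for a within-between interaction, not overall change, so that ratio has no meaning here.

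**Conclusion.** The point holds for the time effect. The higher-missingness rule rests on a question that observed data cannot settle, ends in imputation whatever the answer, and has no sensitivity analysis behind it, in a study that expects to lose 30%. Sections 5.2.1 and 8.2 do not settle who is imputed and who is dropped. If drop-out depends on unseen distress, the fall in DASS-21 could be overstated by about 0.07 to 0.29 SD with imputation under missing at random, or about 0.04 to 0.18 SD with exclusion. These ranges rest on assumed log-scale drop-out slopes of 0.5 to 1.5 per SD and correlations of 0.5 to 0.75.

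A reader might extend this to the interaction on which the sample size was based. The check does not support that unless drop-out differs between the groups. The time effect still matters, because the primary objective is a reduction in distress. The plan should be changed, but the documents do not show that its result will be wrong.

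**What to change.** 1. In section 8.2, remove the 5% threshold and the missing-at-random check as decision rules. State missing at random as the working assumption of the primary analysis. A comparison of drop-outs with completers may stay as description.
2. Reconcile sections 5.2.1 and 8.2. Use every observed DASS-21 score from all participants who have not asked for their data to be removed. An analysis limited to those who attended all sessions can be secondary.
3. Keep the group factor and the group-by-time interaction. Use multiple imputation with baseline score, session-3 score and group in the model, or an equivalent mixed model. Either still assumes missing at random, so neither replaces step 4.
4. Pre-specify one sensitivity analysis: impute missing six-week scores with a worsening shift in steps, and report the shift at which the conclusion on change over time alters. The biases above correspond to shifts of 0.07/0.30 = 0.23 SD to 0.29/0.30 = 0.97 SD, so steps of 0.25 SD from 0 to 1 SD would cover them.

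Cost: a paragraph or two of wording, an amendment by the route in section 12.1, and a few hours of analysis. No new data are needed. The downside is one more sensitivity result to report.

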9 ADVERSE EVENTS

Should multiple participants present with high levels of persistent distress that appear to be related to participating in the group, this will be reviewed by the Chief investigator and researchers.

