The study will aim to ensure that all participants have capacity to give informed consent and that they are not pressured into participating. Confidentiality will be maintained where appropriate, with safeguarding measures in place to safely manage any disclosures that occur during the study. It is possible that by participating in the group, focus group or completing the study questionnaires, that participants may experience some distress. This will be safely managed by signposting participants and communicating with their GP as appropriate. However, participants also may benefit from the therapeutic group and consequently experience a reduction in psychological distress and a possible improvement in their child's wellbeing. Participants may also derive some satisfaction from their involvement in the research.

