5.2.1 Withdrawal of Study Participants

Participants are free to withdraw from the study at any point or a participant can be withdrawn by the Investigator. If withdrawal occurs, the primary reason for withdrawal will be documented in the participant's case report form, if possible. The participant will have the option of withdrawal from

- (i) all aspects of the trial but continued use of data collected up to that point
- (ii) all aspects of the trial with removal of all previously collected data

Participants who do not attend one or more of the group sessions will be welcome to attend the remaining sessions if they so wish but will be excluded from any relevant analyses. Participants may take part in the focus group if they have attended at least one group session.

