11.2.5 Confidentiality

Participants' confidentiality will be maintained by ensuring that any identifiable information collected during the study is not accessible by any non-NHS staff, with the identifiable information kept within NHS Lothian. Participants will be informed in the participant information sheet that all information is confidential, but that their GP will be notified that they are participating in the study and that should the researchers become aware that there is a risk of harm to the participant or to someone else their GP and other relevant professionals will be notified (e.g. Police Scotland; Social Work Services). We will manage the identification of suicidal ideation or other significant mental health difficulties in participants by providing the participant with suitable contact numbers for support after the group session and notifying their GP by phone. In instances where child protection concerns are identified, the Clinical Supervisor and relevant NHS Child Protection Liaison will be consulted as soon as possible, and Social Work Services contacted by phone as per NHS Lothian child protection guidelines if appropriate. In the unlikely event of the researcher being made aware of a serious crime, Police Scotland will be contacted by phone should this be deemed to be in the public interest, as per confidentiality/data protection guidelines.

While given the group setting it may be difficult to ensure confidentiality is maintained by other participants, the importance of this will be emphasised at the beginning of each group and will be part of the "group rules".

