12.3 SERIOUS BREACH REQUIREMENTS

A serious breach is a breach which is likely to effect to a significant degree:

- (a) the safety or physical or mental integrity of the participants of the trial; or
- (b) the scientific value of the trial.

If a potential serious breach is identified by the Chief investigator, Principal Investigator or delegates, the co-sponsors ([contact]) must be notified within 24 hours. It is the responsibility of the co-sponsors to assess the impact of the breach on the scientific value of the trial, to determine whether the incident constitutes a serious breach and report to research ethics committees as necessary.

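### Section 9 requires review only when several participants have related persistent distress; the protocol specifies no study-level record or review of a single related case

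*Combined protocol and SAP*

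**What the plan says.** Section 9 is a single sentence. Its condition is "Should multiple participants present with high levels of persistent distress that appear to be related to participating in the group", and its consequence is "this will be reviewed by the Chief investigator and researchers". It names no log, timeline, grading of seriousness or causality, or report to the sponsor or ethics committee. The terms SAE, SAR and SUSAR are in the list of abbreviations and are not used in the body.

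The protocol foresees the risk. Section 1.1 (Study Risks and Benefits) accepts that, through the group, the focus group or the questionnaires, "participants may experience some distress". Its response is "This will be safely managed by signposting participants and communicating with their GP as appropriate". For suicidal ideation or other significant mental health difficulty, Section 11.2.5 specifies "providing the participant with suitable contact numbers for support after the group session and notifying their GP by phone". For child protection concerns, the same section says that "the Clinical Supervisor and relevant NHS Child Protection Liaison will be consulted as soon as possible".

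**The concern.** The intervention aims to reduce distress, and the protocol names distress as a possible effect of taking part. In a study of about 40 people, related serious events are likely to be few, so the case that most needs a rule is the first one. Section 9 sets its threshold above that case.

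Two things are at stake. One is oversight. Section 3 expects some participants to wait for a suitable group, and Section 5.1 refers to flyers giving the next group dates, so groups appear to be staggered. A single related case in an early group need not be looked at before a later one starts. The other is harms reporting. Section 8.2 plans means, standard deviations, ranges and ANOVA, with no count of participants who came to harm. Section 5.2.1 excludes anyone who misses a session from relevant analyses. A participant who stops attending because of distress could therefore fall outside both the required review and the reported results.

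**Working it through.** **Step 1: look for any other provision that covers a single related case.** Each candidate is set against what it would need to do.

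| Section | What sets it off | What follows | Fills the gap? |
|---|---|---|---|
| 1.1, Study Risks and Benefits | One distressed participant | Signposting, GP contact | No: care, no study record |
| 11.2.5, mental health | One participant with suicidal ideation or significant difficulty | Contact numbers, GP call | No: care, no study record or relatedness review |
| 11.2.5, child protection | One safeguarding concern | Clinical Supervisor and NHS liaison consulted | No: a safeguarding route |
| 5.2.1 | A withdrawal | "If withdrawal occurs, the primary reason for withdrawal will be documented in the participant's case report form, if possible" | Only if the person leaves, and only where possible |
| 12.2 | A deviation or violation | Deviation log, report to sponsor | No: harm can occur without a deviation |
| 12.3 | "A serious breach is a breach which is likely to effect to a significant degree" | Co-sponsors notified | No: harm can occur without a breach |
| 10.2 | Sponsor risk assessment under sponsor SOPs | Monitoring and audit plans | Not known: these are not in the documents |

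Nothing in the text requires a single related event to be recorded, assessed for relatedness or reviewed at study level.

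**Step 2: illustrate how often the threshold would matter.** Section 9 contains no figure to reproduce. The inputs are:
- n = 40, from Section 4.1 (4 groups × 10 participants = 40).
- p, the chance that a participant has distress meeting every part of Section 9's condition except the number of people. The documents give no value. Assumed: 1%, 2.5%, 5% and 10%.
- Independence between participants. Assumed.
- Multiple is read as two or more. Assumed; a reading of three or more would widen the gap.

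Formulas:
- P(0) = (1 − p)^40
- P(exactly 1) = 40 × p × (1 − p)^39
- P(2 or more) = 1 − P(0) − P(exactly 1)

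For p = 2.5%: P(0) = 0.975^40 = 0.363; P(exactly 1) = 40 × 0.025 × 0.975^39 = 0.373; P(2 or more) = 1 − 0.363 − 0.373 = 0.264.

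| Assumed p | P(0) | P(exactly 1): review not required | P(2 or more): review required | Exactly 1, as a share of trials with any event |
|---|---|---|---|---|
| 1% | 0.669 | 0.270 | 0.061 | 82% |
| 2.5% | 0.363 | 0.373 | 0.264 | 59% |
| 5% | 0.129 | 0.271 | 0.601 | 31% |
| 10% | 0.015 | 0.066 | 0.920 | 7% |

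Rows may differ from 1 in the last digit through rounding. The last column is P(exactly 1) divided by 1 − P(0), taken before rounding.

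**Step 3: place the largest figure in context.** P(exactly 1) is greatest at p = 1/n = 1/40 = 2.5%. The 37% is therefore the maximum over all rates, not a typical value.

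**The case against.** Section 9 says when review is required; it does not forbid review of one case. Under Section 11.2.5 the study researchers are the people who learn of a risk and telephone the GP, so the study team would know. Other traces may exist: three DASS-21 scores, the open-ended workshop evaluation items, the focus group, and a withdrawal reason. Section 11.1 commits to ICH GCP principles, and the sponsor SOPs and risk assessment in Section 10.2 might add a reporting duty. Two participants in one group could meet the trigger, so an early signal is not always missed. The event rates have no source, and group-related distress may cluster within workshops, which the binomial ignores.

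Most of this stands as a limit on wording. A reader might infer that a single case would leave no trace, would never be reviewed or would get no response. The documents do not support that: individual care is specified, and silence about review is not a ban on it. Nor can the 37% be read as the plan's failure rate. It is one point, the highest, on an assumed range.

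What does not stand is the idea that these items fill the gap. None is an adverse-event record, and none obliges anyone to judge whether a single event was related. The unseen SOPs cannot be credited with content that the documents do not show.

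**Conclusion.** The point holds as a gap in what the protocol specifies. Required review starts only with multiple participants, and no study-level recording, relatedness assessment or Chief Investigator review is specified for one related case. This conclusion rests on the text and needs no event rate.

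The illustration shows that the gap is realistic at this sample size. For assumed rates from 1% to 10%, the chance of exactly one event is between 7% and 37%, subject to independence and to reading multiple as two or more. At 5% and above, two or more events are more likely than exactly one.

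The gap touches safety oversight and harms reporting. It does not affect the primary analysis. It is worth correcting because correction is cheap.

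**What to change.** In Section 9:
- Change the trigger for review from multiple participants to each participant.
- Record, under the participant's unique code, every case in which distress leads to the signposting or GP contact already described in Sections 1.1 and 11.2.5.
- Have the Chief Investigator review each coded entry for relatedness.
- Report the counts, including participants who miss sessions or withdraw, unless they choose removal of their data under Section 5.2.1.

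The log must be coded because Section 11.2.5 keeps identifiable information from non-NHS staff and limits the identifiable electronic folder to the researcher and clinical supervisor. Section 12.7 can be read as placing the Chief Investigator in the University. The amended text should state who may see the log.

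A count of participants whose DASS-21 worsens is optional. It needs no new data, but it needs a threshold stated in advance, since counting any increase would include ordinary score fluctuation. It should be reported as descriptive only: the protocol describes no untreated control, so the count cannot show that the workshop caused the change.

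Individual care stays as the protocol describes. The cost is a few lines in Section 9, one coded log, a short table of counts and minor administrative time.
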